### **9.3.2 Patient Disposition**

An accounting of study patients by disposition will be tabulated and the number of patients in each analysis set will be summarized. Patients who discontinue study treatment and patients who withdraw from the study will be summarized with reason for discontinuation or withdrawal.

### **9.3.3 Patient Characteristics**

Demographics and other baseline characteristics will be summarized. Details will be provided in the SAP.

### **9.3.4 Treatment Compliance**

The dose administered at each cycle for each treatment agent will be assessed and dose intensity may be summarized. Details will be provided in the SAP.

### **9.3.5 Efficacy Analyses**

All efficacy endpoints will be analyzed using the ITT analysis set. Supplemental analyses will be performed using the mITT analysis set.

#### **9.3.5.1 Primary Efficacy Analysis**

**CRc rate** will be analyzed based on the ITT analysis set. The CRc rate between the 2 treatment arms will be compared using a Cochran-Mantel-Haenszel test stratified by the randomization strata. The CRc rate and its 2-sided 99% confidence interval (CI) will be summarized by treatment arm. At the time of the primary analysis of CRc rate, only the first 308 patients randomized will be included in the population for the analysis of CRc rate. CRc rate will also be analyzed for all randomized patients at the time of the final analysis.

**Overall survival** will be assessed using Kaplan-Meier methods. A stratified log-rank test without adjustments for covariates will be used in the primary evaluation of OS differences between the 2 treatment arms based on the ITT population. The hazard ratio will be estimated using the unadjusted stratified Cox model. The 2-sided 95% CI and the CI corresponds to the significance level of the test following the multiplicity adjustment (see Section [9.3.1.5](#)) will be presented. The proportional hazard assumptions will be examined and sensitivity analyses

will be conducted if appropriate. All events entered in the database at the time of the analysis and source-data verified will be included in the analysis of OS, even if there is more than the pre-specified number of events.

Kaplan-Meier curves depicting OS in the 2 treatment arms will be generated. Additionally, the median OS and the probability of OS from 1 month to the end of the follow-up period will be reported at pre-specified intervals. The associated 2-sided 95% CIs will be calculated using the complementary log-log transformation method (Collett 1994). Detailed methodology will be provided in the SAP.

### 9.3.5.2 Secondary Efficacy Analyses

**MRD-negative CRc rate:** MRD-negative CRc rate will be analyzed based on the ITT analysis set. The MRD-negative CRc rate between the 2 treatment arms will be compared using a Cochran-Mantel-Haenszel test stratified by the randomization strata. The MRD-negative CRc rate and its 2-sided 95% CI will be summarized by treatment arm.

**Duration of remission:** Duration of remission will be analyzed using Kaplan-Meier methodology and Kaplan-Meier plots will be provided by treatment arm using the ITT analysis set. The median remission duration and its 2-sided 95% CI using the complementary log-log transformation method (Collett 1994) will be calculated by treatment arm.

**Event-free survival:** EFS will be analyzed using Kaplan-Meier methodology and Kaplan-Meier plots will be provided by treatment arm using the ITT analysis set. The median EFS and its 2-sided 95% CI using the complementary log-log transformation method (Collett 1994) will be calculated by treatment arm.

**Leukemia-free survival:** LFS will be analyzed using Kaplan-Meier methodology and Kaplan-Meier plots will be provided by treatment arm using the ITT analysis set. The median LFS and its 2-sided 95% CI using the complementary log-log transformation method (Collett 1994) will be calculated by treatment arm.

**Time to complete remission:** TTCR will be summarized by treatment arm using descriptive statistics.

### 9.3.6 Pharmacokinetic, ATA, and Biomarker Analyses

Observed plasma vadastuximab talirine ADC and SGD-1882 (if measurable) will be summarized with descriptive statistics at each PK sampling timepoint. These data may be combined with data from previous studies for population PK and PK/PD analyses. The relationship between vadastuximab talirine PK and PD endpoints, safety, or efficacy may be explored; these analyses, if conducted, will be descriptive.

The incidence of ATA will be summarized by descriptive statistics.

Biomarker assessments will also be summarized using descriptive statistics.

### **9.3.7 Patient Reported Outcomes Analyses**

PRO analyses will be conducted using the ITT analysis set and will assess the change from baseline to the end of treatment in PRO assessments. QLQ-C30 scores will be determined per patient self-report. Change from baseline to end of treatment in QLQ-C30 scores will be summarized using descriptive statistics.

EQ-5D Health Index Scores will be determined by patient self-report. The EQ-5D health state index and visual analog scale will be summarized descriptively by visit.

### **9.3.8 MRU Analyses**

MRU data will be summarized using descriptive statistics. Details will be provided in the SAP.

### **9.3.9 Safety Analyses**

All safety analyses will be performed using the safety analysis set unless otherwise specified.

#### **9.3.9.1 Extent of Exposure**

Duration of treatment, number of cycles, total dose and dose intensity may be summarized by treatment agent and arm. Dose modifications will also be summarized. Details will be provided in the SAP.

#### **9.3.9.2 Adverse Events**

Adverse events will be defined as treatment emergent if they are newly occurring or worsen following study treatment. The incidence of all AEs, treatment-emergent AEs, and treatment-related AEs will be tabulated. AEs will be classified by system organ class and preferred term using the Medical Dictionary for Regulatory Activities (MedDRA).

AEs will be listed and summarized by treatment arm, MedDRA preferred term, severity, and relationship to study drug. In the event of multiple occurrences of the same AE with the same preferred term in one patient, the AE will be counted once as the occurrence. The incidence of AEs will be tabulated by preferred term and treatment group. AEs leading to premature discontinuation of study drug will be summarized and listed in the same manner.

#### **9.3.9.3 Deaths and Serious Adverse Events**

Serious adverse events will be listed and summarized in the same manner as all AEs. Events with a fatal outcome will be listed.

#### **9.3.9.4 Clinical Laboratory Results**

Summary statistics for actual values and for change from baseline may be tabulated as appropriate for selected laboratory results by treatment arm and scheduled visit. Patients with laboratory values outside of the normal reference range at any postbaseline assessment will be listed.

### **9.3.9.5 Other Safety Analyses**

#### **ECOG Status**

ECOG status may be summarized for each visit. Shifts from baseline to the best and worst postbaseline score may be tabulated.

#### **Vital Signs**

Vital signs will be summarized. Changes in vital sign measurements from pre-dose to post-dose of blinded study treatment may be tabulated.

#### **Hospitalizations**

Hospitalization data will be summarized. Details will be provided in the SAP.

#### **Transfusions**

RBC and platelet transfusion independence will be summarized. Details will be provided in the SAP.

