**Table 1: Dose modifications for blinded study treatment-associated toxicity**

Category	Event	Action
Hematologic toxicity in the absence of leukemia (CR, CRi, morphologic leukemia-free state [mLFS]; see Appendix E )	≥ Grade 3 neutropenia or thrombocytopenia	Cycles of blinded study treatment must be delayed up to 28 days b until hematologic recovery is observed. Adequate hematologic recovery is defined as ANC < Grade 3, and rising and/or platelets < Grade 3 (unsupported).  Dose reduction of blinded study treatment to 5 mcg/kg is permitted after any dose delay, and is required if a second dose delay occurs. Treatment must be discontinued for delays of >56 days after dose reduction, unless approved by the medical monitor.
Hematologic toxicity with persistent leukemia a	≥ Grade 3 neutropenia or thrombocytopenia	Blinded study treatment may continue without dose modification.
Non-hematologic toxicity or non-hematologic laboratory abnormality (with the exception of hepatic toxicity)	≥ Grade 3 event	Treatment delay of up to 14 days is required b until resolution of toxicity to < Grade 3.
Laboratory evidence of hepatic toxicity (elevation in ALT, AST, or total bilirubin)	≥ Grade 3 event	Treatment delay of up to 14 days is required until resolution of toxicity to ≤ Grade 1 or baseline. If toxicity has not resolved within 14 days, must permanently discontinue blinded study treatment.

a Blasts are at least 5% in bone marrow by morphology, circulating blasts are present, or there is evidence of extramedullary leukemia

b Delays of >14 days may be permitted with approval of the medical monitor

HMA dose modifications are at the discretion of the treating physician and should adhere to the HMA package insert or Summary of Product Characteristics (SmPC) or institutional guidelines/standards. If dosing is delayed for either blinded study treatment or HMA, both should be held and resumed together on the same schedule.

Blinded study treatment or HMA treatment may be permanently discontinued in the event of unacceptable treatment-related toxicity. Patients will not be considered off treatment until both blinded study treatment and HMA have been discontinued.

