## **5.5 Concomitant Therapy**

All concomitant medications, blood products, and radiotherapy administered will be recorded from Day 1 (predose) through the safety reporting period. Any concomitant medication given for a study protocol-related adverse event should be recorded from the time of informed consent.

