7.6.4 Concomitant Medications

Concomitant medications will be summarized by the WHO Drug substance name by treatment group and total, and listed by patient.

The number and percentage of patients who receive myeloid growth factor as a concomitant medication and the reason for administration will be summarized by treatment group and total.

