9.2.3 Version 4 Changes

The study was terminated early due to safety concerns raised by the IDMC. The SAP was updated to include only analyses required for the abbreviated CSR. Changes from version 3 are summarized below:

- Sec 6.7: Clarify that all efficacy analyses will be descriptive in nature and no multiple testing procedure will be applied
- Sec 6.10: Clarify that no interim analysis will be conducted and final analysis will be based on 240 patients randomized into the study by the time enrollment was closed
- Sec 7.1: Remove the summary of screen failed patients
- Sec 7.5: Remove all efficacy analyses other than the descriptive summary of CRc rate, OS, MRD-neg CRc rate, and early mortality rate
- Sec 7.6.1: Add additional summary of AEs of special interest
- Sec 7.6.2: Add additional summary to evaluate the extent of neutropenia
- Sec 7.7: Remove the analyses of PRO endpoints, transfusion, MRU, and subsequent therapy
- Sec 8: Clarify that no interim analysis will be conducted and final analysis will be based on 240 patients randomized into the study by the time enrollment was closed

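### The SAP drops the protocol's transfusion-independence safety summary and does not list this as a change from the protocol, so transfusion burden by arm goes unreported

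*Protocol*

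**What the plan says.** Protocol 9.3.9.5, Other Safety Analyses, has a Transfusions entry: "RBC and platelet transfusion independence will be summarized". It leaves the detail to the SAP. The data are to be collected under Protocol 5.5: "All concomitant medications, blood products, and radiotherapy administered will be recorded from Day 1 (predose) through the safety reporting period". Protocol 7.6 also gives transfusion requirements as an example of medical resource utilization (MRU) data.

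The current SAP has no transfusion analysis in sections 7.1 to 7.7. Its change log for version 4 (section 9.2.3) has the entry "Remove the analyses of PRO endpoints, transfusion, MRU, and subsequent therapy", with a general reason: "The SAP was updated to include only analyses required for the abbreviated CSR". SAP 9.1, which is the place for changes from the protocol, says that the heading does not apply.

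Three related analyses remain in the SAP:
- Section 7.6.1 summarizes adverse events in search categories that include thrombocytopenia and anemia, by maximum severity.
- Section 7.6.2 gives laboratory values and change from baseline by scheduled visit, and shifts from baseline to the worst post-baseline CTCAE grade. It has no rule for values taken after a transfusion.
- Section 7.6.4 summarizes concomitant medications by substance. For neutrophil support it adds "The number and percentage of patients who receive myeloid growth factor as a concomitant medication", with the reason for use.

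**The concern.** Thrombocytopenia and anemia are expected harms. Protocol 1.5 reports Grade 3 or higher events in 21% and 25% of the 24 patients in the phase 1 combination cohort. Transfusion need is a direct measure of how much marrow suppression costs the patient, and the protocol planned to report it as safety. The removal closes both planned routes, the transfusion-independence summary and the MRU summary.

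Transfusion also raises the measured platelet count or hemoglobin. If the arm with worse suppression is transfused more, its by-visit values are raised more, and a reader of those tables has no means of seeing it. The study was terminated for safety concerns raised by the IDMC, so safety is the main content of the abbreviated report.

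**Working it through.** The documents state no figure for transfusions, so there is nothing to reproduce. The check sets the sections side by side.

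1. **Commitment against current plan.** Protocol 9.3.9.5 is worded as a firm plan. SAP 7.1 to 7.7 contains nothing that meets it. SAP 9.2.3 discloses the removal, but SAP 9.1 does not list it. The omission is therefore deliberate, and 9.1 is inaccurate.

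2. **Are the data there?** Under Protocol 5.5 and 7.7.1.3, blood products are recorded from before the first dose to the later of the end-of-treatment visit and 30 days after the last study treatment. This does not depend on long efficacy follow-up. Limited data availability is the reason given for version 5 (SAP 9.2.4), but transfusion had already gone at version 4.

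3. **Do the remaining tables carry the information?**
   - *Adverse events:* each patient counts once per preferred term, at the highest severity. Number and duration of transfusions do not appear.
   - *Concomitant medications:* SAP 7.6.4 does not say whether blood products enter the substance table. If they do, the table shows at best whether a patient ever received the product.
   - *Illustration, on assumed rates:* if a proportion p of the comparator arm is ever transfused, the experimental arm can exceed it by at most 1 − p. For p = 0.80 this is 1 − 0.80 = 0.20, and for p = 0.95 it is 1 − 0.95 = 0.05, that is, 20 to 5 percentage points. A patient transfused twice weekly (also assumed) receives 2 × 4 = 8 transfusions over 28 days and 2 × 8 = 16 over 56 days, the two delay lengths in Protocol Table 1. Each such patient counts the same as one given a single unit.

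4. **By-visit means.** Write u for an arm's mean unsupported level, f for the share of its values taken under transfusion support, and d for the mean rise that support gives. The tabulated mean is u + f·d. The tabulated comparator-minus-experimental difference is then (u_C − u_E) − (f_E·d_E − f_C·d_C). It understates the true difference whenever f_E·d_E exceeds f_C·d_C. The documents give neither f nor d, so the direction is conditional and the size is unknown.

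5. **Worst grade.** A later transfused value cannot remove an earlier recorded low value from a worst-grade shift table. A low value can be missed only if it was seen locally and a transfusion came before the scheduled central sample. Protocol 7.7.2 assigns scheduled safety tests to the central laboratory and clinical decisions to local testing; SAP 7.6.2 does not say whether local values enter. Under Protocol 6.3, blood counts are dense in Cycles 1 and 2 (Days 1, 5 or 7, 15 and 21). From Cycle 5, a patient in CR or CRi has them on Day 1 and at the few occasions tied to a marrow examination. The gap is therefore possible, mainly in later cycles, but it is not shown to be large.

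6. **Recovery definitions.** Appendix E requires no transfusion within 7 days for CR, and classes a platelet count of at least 100,000/µL in a recently transfused patient as CRi(p). Table 1 counts platelet recovery only if unsupported. The SAP has no other platelet or hemoglobin recovery analysis.

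**The case against.** The removal is permitted and disclosed. Protocol 9.3 allows analysis changes without an amendment unless site conduct changes, the transfusion detail was left to the SAP, and the version 4 log gives early termination and an abbreviated report as the reason. Grouping transfusion with MRU has a basis in Protocol 7.6. Cytopenias are still reported through Grade 3 or higher events, serious events, the named search categories, worst-grade shifts and a listing of Grade 3 or higher laboratory results. Protocol 7.7.1.1 allows a laboratory abnormality that needs an intervention to be recorded as an adverse event, and a transfusion is naturally read as one. The contrast with growth factors is also modest, since version 5 removed their cumulative-dose summary.

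All of this stands, and it limits the point. A reader might infer more: that transfused counts pass as recovery, or that thrombocytopenia and anemia are under-reported. The documents do not support either. The recovery definitions exclude or separately class supported platelet counts, and the worst-grade and adverse-event routes do not depend on by-visit means.

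The objection does not supply a measure of transfusion burden. The change log gives no specific reason for dropping a safety item whose data are collected. Patient-level listings and submitted datasets allow someone to reconstruct the burden, but they do not report it.

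**Conclusion.** The point holds in limited form. A firm protocol safety analysis is absent from the current SAP, section 9.1 does not acknowledge it, and no remaining table reports transfusion burden by arm. By-visit platelet and hemoglobin summaries can understate an arm difference in marrow suppression, on the assumption that the worse arm is transfused more. The 5 to 20 point bound and the 8 to 16 transfusions rest on assumed rates and show only why ever/never use is a coarse measure; they do not estimate a bias. Severity is minor: cytopenia events and worst grades are still reported, and all efficacy analyses are already descriptive. It is a cheap improvement to a report whose main subject is safety.

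**What to change.** - **Restore a short summary in SAP 7.6**, by arm on the safety set, from the blood-product records. Give RBC and platelet transfusions per patient-month of the recording period, ending at death if that comes first, which allows for unequal follow-up. Give the number and percent transfusion independent, separately for RBC and platelets. State the required transfusion-free interval in advance, and say how patients who die before completing it, and survivors observed for less than it, are counted. Otherwise early death or short follow-up could pass as independence.
- **Flag, but do not exclude,** platelet and hemoglobin values within 7 days after a transfusion, and show the number and percent flagged by visit and arm in SAP 7.6.2. The window is already in Appendix E for blood count recovery; its use for hemoglobin is an extension. Exclusion would be worse: a patient transfused twice weekly would contribute no values during that time, so the most cytopenic patients would drop out and the worse arm's remaining mean would rise.
- **Correct SAP 9.1** to list any protocol analysis that stays removed, with its reason.

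The cost is SAP wording and two or three extra tables in an abbreviated report. No new data and no change to clinical conduct are needed. If the sponsor keeps the removal, the correction to 9.1 is the minimum.

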### **9.3.10 Interim Analyses**

An IDMC will periodically monitor the trial for safety, including SAEs and early mortality, during the treatment period. During the periodical safety review, the IDMC will evaluate the 60-day mortality rates in the 2 treatment arms. The independent statistician will assist the IDMC to evaluate whether there is an increased risk of early death in the experimental arm and make appropriate recommendations to the sponsor.

Two formal interim analyses for OS are planned for the study. The first interim analysis is for the purpose of futility testing and will be conducted when approximately 106 OS events have occurred (~30% of the targeted number of events). The second interim analysis is for superiority testing and will occur in conjunction with the primary analysis of CRc rate. The analysis will be conducted when the following 2 conditions are met: 1) 6 months after 308 patients have been randomized, and 2) approximately 212 OS events have occurred (~60% of the targeted number of events). The stopping boundaries will be determined using Lan-DeMets spending functions to simulate O'Brien-Fleming boundaries. Details will be provided in the SAP.

The IDMC will provide recommendations to the sponsor's Data Review Board as to appropriate study direction. The sponsor will remain blinded to treatment assignment. See the IDMC Charter for details.

## **10 INFORMED CONSENT, ETHICAL REVIEW, AND REGULATORY CONSIDERATIONS**

This study will be conducted in accordance with the Note for Guidance on GCP (ICH Harmonized Tripartite Guideline E6 (R1); FDA CFR [21 CFR § 50, 56, 312]), Declaration of Helsinki (Brazil 2013), and all applicable regulatory requirements.

### **10.1 Informed Consent**

The investigator is responsible for presenting the risks and benefits of study participation to the subject in simple terms using the IRB/IEC approved informed consent document and for ensuring patients are re-consented when the informed consent document is updated during the study, if required. The investigator will ensure that written informed consent is obtained from each patient by obtaining the signature and date on the informed consent document prior to the performance of protocol evaluations or procedures.

### **10.2 Ethical Review**

The investigator will provide the sponsor or its designee with documentation of the IRB/IEC approval of the protocol and the informed consent document before the study may begin at the investigative site(s). The name and address of the reviewing ethics committee are provided in the investigator file.

The investigator will supply the following to the investigative site's IRB/IEC:

- Protocol and amendments
- Informed consent document and updates
- Clinical Investigator's Brochure and updates
- Relevant curricula vitae, if required
- Required safety and SAE reports
- Any additional submissions required by the site's IRB/IEC

The investigator must provide the following documentation to the sponsor or its designee:

- The IRB/IEC periodic (e.g., quarterly, annual) re-approval of the protocol.
- The IRB/IEC approvals of any amendments to the protocol or revisions to the informed consent document.
- The IRB/IEC receipt of safety and SAE reports, as appropriate.

